9.7 Evaluation of Best Overall Response

NOTE: Revise table if response rate is primary objective of the study, and confirmation of response is required. See Eur J Cancer 45;2009:228-247 for complete details.

Target Lesions	Non-Target Lesions	New Lesions	Overall Response
CR	CR	No	CR
CR	Non-CR/ Non-PD	No	PR
CR	Not evaluated	No	PR
PR	Non-PD/ or not all evaluated	No	PR
SD	Non-PD or not all evaluated	No	SD
Not all evaluated	Non-PD	No	Non-evaluable
PD	Any	Yes or No	PD
Any	PD*	Yes or No	PD
Any	Any	Yes	PD
*In exceptional circumstances, unequivocal progression in non-target lesions may be accepted as disease progression.			

Subjects with a global deterioration of health status requiring discontinuation of treatment without objective evidence of disease progression at that time should be classified as having “symptomatic deterioration.” Every effort should be made to document the objective progression even after discontinuation of treatment.

In some circumstances, it may be difficult to distinguish residual disease from normal tissue. When the evaluation of complete response depends on this determination, it is recommended that the residual lesion be investigated (fine needle aspirate/biopsy) to confirm the complete response status.

9.8 Definitions for Response Evaluation – RECIST 1.1

9.8.1 First Documentation of Response

The time between initiation of therapy and first documentation of PR or CR.

9.8.2 Confirmation of Response

To be assigned a status of complete or partial response, changes in tumor measurements must be confirmed by repeat assessments performed no less than four weeks after the criteria for response are first met.

9.8.3 Objective Response Rate

The objective response rate is the proportion of all subjects with confirmed PR or CR according to RECIST 1.1, from the start of treatment until disease progression/recurrence (taking as reference for progressive disease the smallest measurements recorded since the start of treatment).

9.8.4 Time to Progression

A measurement from the date of registration until the criteria for disease progression is met as defined by RECIST 1.1. Subjects who have not progressed or have died due to any cause will be right-censored at the date of the last disease evaluation or date of death.

9.8.5 Progression Free Survival

A measurement from the date of registration until the criteria for disease progression is met as defined by RECIST 1.1 or death occurs. Subjects who have not progressed will be right-censored at the date of the last disease evaluation.

9.8.6 Overall Survival

Overall survival is defined by the date of registration to date of death from any cause.

9.9 Immune-Related RECIST (irRECIST)

9.9.1 Measurable Lesion Definitions and Target Lesion Selection

Follow the definitions from RECIST 1.1. Measurable lesions must be accurately measured in at least one dimension with a minimum size of:

- 10 mm in the longest diameter by CT or MRI scan (or no less than double the slice thickness) for non-nodal lesions and ≥ 15 mm in short axis for nodal lesions
- 10 mm caliper measurement by clinical exam
- 20 mm by chest X-ray
- At the baseline tumor assessment, the sum of the products of the two largest perpendicular diameters (SPD) of all index lesions (five lesions per organ, up to 10 visceral lesions and five cutaneous index lesions) is calculated.
- Baseline: Target and Non-Target Lymph Node Lesion Definitions - Follow the definitions from RECIST 1.
- Baseline: Bone Lesions- Follow the definitions from RECIST 1.1. Regardless of the imaging modality blastic bone lesions will not be selected as target lesions. Lytic or mixed lytic-blastic lesions with a measurable soft tissue component ≥ 10 mm can be selected as target lesions.
- Baseline: Cystic and necrotic lesions as target lesions that are partially cystic or necrotic can be selected as target lesions. The longest diameter of such a lesion will be added to the Total Measured Tumor Burden (TMTB) of all target lesions at baseline. If other lesions with a non-liquid/non-necrotic component are present, those should be preferred.
- Baseline: Lesions with prior local treatment during target lesion selection the radiologist will consider information on the anatomical sites of previous intervention (e.g. previous irradiation, RF-ablation, TACE, surgery, etc.). Lesions undergoing prior intervention will

not be selected as target lesions unless there has been a demonstration of progress in the lesion

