9.9.7 Cystic and Necrotic Lesions as Target Lesions

Lesions that are partially cystic or necrotic can be selected as target lesions. The longest diameter of such a lesion will be added to the Total Measured Tumor Burden (TMTB) of all target lesions at baseline. If other lesions with a non-liquid/non-necrotic component are present, those should be preferred.

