9.9.9 Follow-up

- Only index and measurable new lesions are taken into account. The longest diameters of non-nodal target and new non-nodal measurable lesions, and short axes of nodal target

and new nodal measurable lesions will be recorded. Together they determine the Total Measured Tumor Burden (TMTB) at follow-up.

- Definition of Measurable New Lesions: In order to be selected as new measurable lesions (≤ 2 lesions per organ, ≤ 5 lesions total, per timepoint), new lesions must meet criteria as defined for baseline target lesion selection and meet the same minimum size requirements of 10 mm in long diameter and minimum 15 mm in short axis for new measurable lymph nodes. New measurable lesions shall be prioritized according to size, and the largest lesions shall be selected as new measured lesions.
- Non-Target Lesion Assessment- The RECIST 1.1 definitions for the assessment of non-target lesions apply. The response of non-target lesions primarily contributes to the overall response assessments of irCR and irNon-CR/Non-PD (irNN). Non-target lesions do not affect irPR and irSD assessments. Only a massive and unequivocal worsening of non-target lesions alone, even without progress in the TMTB is indicative of irPD.
- New Non-Measurable Lesions Definition and Assessment: All new lesions not selected as new measurable lesions are considered new non-measurable lesions and are followed qualitatively. Only a massive and unequivocal progression of new non-measurable lesions leads to an overall assessment of irPD for the timepoint. Persisting new non-measurable lesions prevent irCR

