9.9.10 Evaluation of Best Overall Response per irRECIST

% Change in Sum of the Diameters	Target Lesion Definition	Non-Target Lesion Definition	New Measurable Lesions	New Unmeasurable Lesions	Overall Modified RECIST Timepoint Response
-100% ^a	CR	CR	No	No	CR
-100% ^a	CR	Non-CR or not all evaluated	No	No	PR
$\leq -30\%$	PR	Any	Yes or no	Yes or no	PR
$> -30\%$ to $< +20\%$	SD	Any	Yes or no	Yes or no	SD
Not all evaluated	Not evaluated	Any	Yes or no	Yes or no	NE
$\geq \pm 20\%$	PD	Any	Yes or no	Yes or no	PD

CR =complete response; NE= not evaluable; PD=progressive disease; PR =partial response; RECIST =Response Evaluation Criteria in Solid Tumors; SD= stable disease.

^a When lymph nodes are included as target lesions, the % change in the sum of the diameters may not be 100% even if complete response criteria are met since a normal lymph node is defined as having a short axis of < 10 mm. Any pathological lymph nodes (whether target or

non-target) must have reduction in short axis to < 10 mm in order to meet the definition of CR. Including Measurable New Lesions When Present.

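### The irRECIST section calculates a baseline sum of products over index lesions, but follow-up and response use sums of diameters of target lesions (minor; secondary endpoint only)

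*Combined protocol and SAP*

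**What the plan says.** Section 9.9.1 opens on a one-dimensional footing: "Follow the definitions from RECIST 1.1. Measurable lesions must be accurately measured in at least one dimension". A later bullet in the same list says that at baseline one calculates "the sum of the products of the two largest perpendicular diameters (SPD) of all index lesions". It limits these lesions to five in any one organ, ten visceral overall and a further five cutaneous.

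The surrounding rules use lengths:

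- **Baseline, partially cystic or necrotic lesions (9.9.1, repeated in 9.9.7):** "The longest diameter of such a lesion will be added to the Total Measured Tumor Burden (TMTB) of all target lesions at baseline".
- **Follow-up (9.9.9):** "The longest diameters of non-nodal target and new non-nodal measurable lesions, and short axes of nodal target" and new nodal lesions are recorded, and together they form the Total Measured Tumor Burden (TMTB).
- **Response (9.9.10):** the classifying column is the percent "Change in Sum of the Diameters", with partial response at -30% or below.

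The lesion set also shifts. Section 9.9.9 begins "Only index and measurable new lesions are taken into account", then names *target* lesions in the next sentence, and later says that "new lesions must meet criteria as defined for baseline target lesion selection". Section 9.3 caps target lesions at 5 in total and 2 per organ, and requires their baseline sum of diameters to be calculated and reported.

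The response rate by irRECIST is a secondary endpoint in sections 2.2.2 and 12.2.2.

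**The concern.** A percent change needs the same quantity, measured on the same lesions, at both times. Within section 9.9 the bullet is the only general instruction for calculating baseline burden, because TMTB at baseline is otherwise mentioned only for cystic or necrotic lesions. Section 9.9.10 does not define its denominator. A reader who looks for one inside section 9.9 finds an area over as many as 15 lesions, and then has to compare it with a length over a set capped at 5.

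At stake is whether the irRECIST response rate can be calculated reproducibly. Readers who resolve the conflict in different ways could place the same scans in different response categories.

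**Working it through.** **Plan's own figure.** The documents give no sample size, power or threshold for the irRECIST response rate, so there is none to reproduce. The Simon design in section 12.3 (3/16, then 11/44, 17% versus 35%) does reproduce: alpha 0.0461 against the stated 0.046, and beta 0.1909 against 0.191. It rests on RECIST 1.1 and is unaffected.

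**Rules side by side**

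| Step | Measure | Lesions |
|---|---|---|
| Baseline, 9.9.1 bullet | products of diameters (area) | index, up to 10 + 5 = 15 |
| Baseline, cystic or necrotic, 9.9.1 and 9.9.7 | longest diameter (length) | target |
| Baseline, 9.3 | sum of diameters (length) | target, up to 5, 2 per organ |
| Follow-up, 9.9.9 | longest diameters and short axes (length) | index in one sentence, target in the next, plus new lesions |
| Response, 9.9.10 | percent change in a sum of diameters | not stated |

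No rule in 9.9.9 or 9.9.10 uses the sum of products (SPD).

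**Size under different readings.** The lesion sizes below are assumed for illustration. The progression cut-off in 9.9.10 is taken as +20%.

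1. *Bullet taken literally: SPD at baseline, diameter at follow-up.* One unchanged lesion of 40 x 30 mm, true change 0%.
   - In millimetres: 40/(40 x 30) - 1 = 40/1200 - 1 = -96.7%.
   - In centimetres: 4/(4 x 3) - 1 = 4/12 - 1 = -66.7%.
   - The answer depends on the recording unit, and section 9.1 allows both.

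2. *SPD at both times with the 9.9.10 cut-offs.* The protocol does not specify this, but a reader might adopt it for consistency. If both diameters change by the same fraction d, the SPD changes by (1 + d)² - 1.
   - Partial response: (1 + d)² = 0.70, so the shrinkage needed is 1 - √0.70 = 16.3%.
   - Progression: (1 + d)² = 1.20, so the growth needed is √1.20 - 1 = 9.5%.
   - Lesions of 40 x 30 and 30 x 20 mm have an SPD of 1200 + 600 = 1800 mm² and diameters of 40 + 30 = 70 mm. A uniform 20% shrinkage is -20% by diameters (stable) but 0.80² - 1 = -36% by SPD (partial response). A uniform 10% growth is +10% by diameters (stable) but 1.10² - 1 = +21% by SPD (progression).
   - The direction can reverse. An elongated lesion going from 40 x 20 to 28 x 22 mm is 28/40 - 1 = -30% by longest diameter (partial response). By SPD it is 616/800 - 1 = -23%, which is not a partial response.

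3. *Diameters at both times, but index lesions at baseline and target lesions at follow-up.* Take ten unchanged 20 mm lesions, five in each of two organs. Baseline is 10 x 20 = 200 mm. With 2 per organ, follow-up is 4 x 20 = 80 mm, so the change is 80/200 - 1 = -60% with no true change.

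4. *Diameters of target lesions at both times.* The two-lesion example, unchanged, gives 70/70 - 1 = 0%, which is stable disease.

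Only the fourth reading gives a sound result and agrees with 9.9.10.

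**The case against.** The best reply is that the text nearly settles the matter itself. The bullet says only that an SPD is calculated; it does not call it the TMTB or the reference for response. A percent change in a sum of diameters needs such a sum at both times, and section 9.3 supplies the baseline one. The opening line of 9.9.1, the cystic-lesion rule, 9.9.7 and 9.9.9 are all linear. On this view the SPD is an unused remnant, *index* is a loose synonym for *target*, and dividing millimetres by square millimetres is an implausible reading.

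Much of that stands. The linear reading is very probably intended, and the figures above illustrate readings rather than predict errors. But the bullet is current text, no passage withdraws it, and 9.9.9 repeats its term *index*, to which only 9.9.1 attaches a number. A definition that readers must infer against a written instruction should be corrected.

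Two further points are fair. Section 12.4.2 calls the response rate it analyses exploratory and does not name irRECIST; that it means this endpoint is an inference. And 9.9.10 has gaps that this correction does not close: it does not say whether progression is measured from baseline or nadir, and it allows any non-target status with stable disease, although 9.9.9 lets massive non-target worsening alone count as progression.

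**Conclusion.** The concern holds, at minor severity. The SPD bullet in 9.9.1 contradicts the diameter-based rules of section 9.9 in its measure, and contradicts section 9.3 in its lesion count (15 against 5).

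The effect on the irRECIST response rate cannot be derived from the documents, and no general direction of bias is claimed. It could be nil if every reader adopts the linear rule.

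The consequences stop at this one endpoint. Assuming section 12.4.2 refers to it, it is reported as an estimate with an exact 95% confidence interval, with no test or threshold attached. The primary response rate and PFS are defined by RECIST 1.1, and neither the Simon rule nor the sample size depends on irRECIST.

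**What to change.** - In 9.9.1, delete the bullet on the SPD of index lesions.
- In its place, define baseline TMTB as the sum of longest diameters (non-nodal) and short axes (nodal) of the target lesions, at most 5 in total and 2 per organ, as in 9.3.
- In 9.9.9, replace *index* with *target*.

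This puts baseline and follow-up on one scale and one lesion set. It should be settled before irRECIST responses are read.

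The cost is wording in section 9.9. Section 9.3 already requires the linear baseline sum, so no new scans or patients are needed. One limit applies: 9.9.1 and 9.9.8 restrict the choice of previously treated lesions and 9.3 does not. The irRECIST target set could therefore differ for some patients, whose existing baseline scans may need re-reading.

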9.9.2 Non-measurable Lesion Definitions

Follow definitions from RECIST 1.1

9.9.3 Non-target lesions will include

- Measurable lesions not selected as target lesions
- All sites of non-measurable disease, such as neoplastic masses that are too small to measure because their longest uninterrupted diameter is < 10 mm (or < two times the axial slice thickness), ie. the longest per-pendicular diameter is ≥ 10 and < 15 mm.
- Other types of lesions that are confidently felt to represent neoplastic tissue, but are difficult to measure in a reproducible manner. These include bone metastases, leptomeningeal metastases, malignant ascites, pleural or pericardial effusions, ascites, inflammatory breast disease, lymphangitis cutis/pulmonis, cystic lesions, ill-defined abdominal masses, skin lesions, etc.

9.9.4 Target and Non-Target Lymph Node Lesion Definitions

Follow definitions from RECIST 1.1

9.9.5 Non-Target Lesion Selection

All lesions or sites of disease not recorded as target lesions should be recorded as non-target lesions at baseline. There is no limit to the number of non-target lesions that can be recorded at baseline.

9.9.6 Bone Lesions

Follow definitions from RECIST 1.1

Regardless of the imaging modality blastic bone lesions will not be selected as target lesions. Lytic or mixed lytic-blastic lesions with a measurable soft tissue component ≥ 10 mm can be selected as target lesions.

9.9.7 Cystic and Necrotic Lesions as Target Lesions

Lesions that are partially cystic or necrotic can be selected as target lesions. The longest diameter of such a lesion will be added to the Total Measured Tumor Burden (TMTB) of all target lesions at baseline. If other lesions with a non-liquid/non-necrotic component are present, those should be preferred.

9.9.8 Lesions with Prior Local Treatment

During target lesion selection the radiologist will consider information on the anatomical sites of previous intervention (e.g. previous irradiation, RF-ablation, TACE, surgery, etc.). Lesions undergoing prior intervention will not be selected as target lesions unless there has been a demonstration of progress in the lesion.

9.9.9 Follow-up

- Only index and measurable new lesions are taken into account. The longest diameters of non-nodal target and new non-nodal measurable lesions, and short axes of nodal target

and new nodal measurable lesions will be recorded. Together they determine the Total Measured Tumor Burden (TMTB) at follow-up.

- Definition of Measurable New Lesions: In order to be selected as new measurable lesions (≤ 2 lesions per organ, ≤ 5 lesions total, per timepoint), new lesions must meet criteria as defined for baseline target lesion selection and meet the same minimum size requirements of 10 mm in long diameter and minimum 15 mm in short axis for new measurable lymph nodes. New measurable lesions shall be prioritized according to size, and the largest lesions shall be selected as new measured lesions.
- Non-Target Lesion Assessment- The RECIST 1.1 definitions for the assessment of non-target lesions apply. The response of non-target lesions primarily contributes to the overall response assessments of irCR and irNon-CR/Non-PD (irNN). Non-target lesions do not affect irPR and irSD assessments. Only a massive and unequivocal worsening of non-target lesions alone, even without progress in the TMTB is indicative of irPD.
- New Non-Measurable Lesions Definition and Assessment: All new lesions not selected as new measurable lesions are considered new non-measurable lesions and are followed qualitatively. Only a massive and unequivocal progression of new non-measurable lesions leads to an overall assessment of irPD for the timepoint. Persisting new non-measurable lesions prevent irCR

9.9.10 Evaluation of Best Overall Response per irRECIST

% Change in Sum of the Diameters	Target Lesion Definition	Non-Target Lesion Definition	New Measurable Lesions	New Unmeasurable Lesions	Overall Modified RECIST Timepoint Response
-100% ^a	CR	CR	No	No	CR
-100% ^a	CR	Non-CR or not all evaluated	No	No	PR
$\leq -30\%$	PR	Any	Yes or no	Yes or no	PR
$> -30\%$ to $< +20\%$	SD	Any	Yes or no	Yes or no	SD
Not all evaluated	Not evaluated	Any	Yes or no	Yes or no	NE
$\geq \pm 20\%$	PD	Any	Yes or no	Yes or no	PD

CR =complete response; NE= not evaluable; PD=progressive disease; PR =partial response; RECIST =Response Evaluation Criteria in Solid Tumors; SD= stable disease.

^a When lymph nodes are included as target lesions, the % change in the sum of the diameters may not be 100% even if complete response criteria are met since a normal lymph node is defined as having a short axis of < 10 mm. Any pathological lymph nodes (whether target or

non-target) must have reduction in short axis to < 10 mm in order to meet the definition of CR. Including Measurable New Lesions When Present.

10. DRUG INFORMATION

10.1 Pembrolizumab (Keytruda®)

Pembrolizumab is a potent and highly selective humanized mAb of the IgG4/kappa isotype designed to directly block the interaction between PD-1 and its ligands, PD-L1 and PD-L2. Keytruda™ (pembrolizumab) has recently been approved in the United States for the treatment of subjects with unresectable or metastatic melanoma and disease progression following ipilimumab and, if BRAF V600 mutation positive, a BRAF inhibitor. It is also approved for the treatment of subjects with PD-L1 positive metastatic NSCLC who have disease progression on or after platinum chemotherapy. Please refer to the current version of the Keytruda® prescribing information and the pembrolizumab Investigator’s Brochure (IB) for additional information regarding this drug.

10.1.1 Supplier/How Supplied

Merck will supply pembrolizumab at no charge to subjects participating in this clinical trial, as summarized in the table below.

Product Name & Potency	Dosage Form
Pembrolizumab 100 mg/ 4mL	Solution for Injection

10.1.2 Preparation

Please refer to the Pharmacy Manual for a comprehensive description of pembrolizumab preparation.

10.1.3 Storage and Stability

Clinical supplies must be stored in a secure, limited-access location under the storage conditions specified on the label.

Clinical supplies may not be used for any purpose other than that stated in the protocol.

10.1.4 Handling and Disposal

Upon completion or termination of the study, all unused and/or partially used investigational product will be destroyed at the site per institutional policy. It is the Investigator’s responsibility to arrange for disposal of all empty containers, provided that procedures for proper disposal have been established according to applicable federal, state, local and institutional guidelines and procedures, and provided that appropriate records of disposal are kept.

10.1.5 Dispensing, Returns and Reconciliation

The investigator is responsible for keeping accurate records of the clinical supplies received from Merck or designee, the amount dispensed to and returned by the subjects and the amount remaining at the conclusion of the trial.

10.1.6 Use in Pregnancy and Nursing Women

Based on its mechanism of action, pembrolizumab can cause fetal harm when administered to a pregnant woman. Subjects who are pregnant or planning to become pregnant are not eligible for enrollment. It is unknown whether pembrolizumab is excreted in human milk. Since many drugs are excreted in human milk, and because of the potential for serious adverse reactions in the nursing infant, subjects who are breast-feeding are not eligible for enrollment.

10.1.7 Adverse Events

Please refer to the current Investigator's Brochure for a complete list of adverse events.

Pembrolizumab is generally well tolerated and demonstrates a favorable safety profile in comparison to chemotherapy. Pembrolizumab is an immunomodulatory agent, and based on this mechanism of action, immune mediated adverse events are of primary concern. Important identified risks for pembrolizumab are of an immune mediate nature, including: pneumonitis, colitis, hypophysitis (including hypothyroidism/hyperthyroidism), hepatitis, Type I diabetes mellitus, uveitis, and nephritis, myositis, Guillain-Barre syndrome, pancreatitis, and severe skin reaction toxic epidermal necrolysis (TEN), some with fatal outcome). A new important risk of myocarditis has been identified; cases with fatal outcome have been reported.

The majority of immune-mediated adverse events were mild to moderate in severity, were manageable with appropriate care, and rarely required discontinuation of therapy.

In addition to the previously noted identified risks, infusion-related reactions are a risk but are not considered immune mediated; these are also further described in the current IB.

